pregnancy testing, when indicated. The laboratory technician will conduct the biomarker analyses for Aim 3. Other personnel include Drs. [name] and [name], who will interpret biomarker data. A statistician from the Johns Hopkins School of Public Health will create the randomization schedule and perform final data analyses.

| | Week 0 | Week 6 | Week 12 | Week 24 | Week 36 | Week 48 |
|-------------------------------------|--------|--------|---------|---------|---------|---------|
| Written consent | Х | | | | | |
| Verify eligibility | Х | | | | | |
| Teaching and First dose | Х | | | | | |
| administration and observation | | | | | | |
| Medical history, relapse assessment | Х | Х | Х | Х | Х | Х |
| Medication review | Х | Х | Х | Х | Х | Х |
| Vital signs | Х | Х | Х | Х | Х | Х |
| Physical, neurologic (EDSS) exams | Х | | X* | X* | | X* |
| MS Functional Composite | Х | Х | Х | Х | Х | Х |
| Adverse event assessment | | Х | Х | Х | Х | Х |
| Biomarker evaluation | Х | Х | Х | Х | Х | Х |
| Stored blood for future studies | Х | Х | Х | Х | Х | Х |
| DXA scan | Х | | | | | |
| A pregnancy test (if woman of | Х | Х | Х | Х | | |
| childbearing potential) | | | | | | |
| MACFIMS battery | Х | | Х | Х | Х | Х |
| Sleep questionnaires | Х | | Х | Х | | Х |
| Depression and quality of life | X | Х | Х | Х | Х | Х |
| Suicidality evaluation | X | X | X | Х | Х | X |

Study Visits: The visit schedule is detailed below. Visits will take place within ± 5 days of the target date.

*EDSS only

Schedule Modification during COVID-19 (will be in effect unless JHU operations have returned to normal, a COVID-19 vaccine has been developed, or evidence of substantial likelihood of herd immunity from COVID-19 due to a high proportion of previously-infected individuals). Additionally, due to COVID-19 and staffing shortages during the holiday season, we will allow study visits within \pm 10 days of the target date if needed to ensure the safety of the participants.

| | Week 0 | Week | Week | Week 24 | Week | Week 48: |
|----------------------------------|--------|---------|------|---------|---------|----------------------|
| | | 6: | 12** | | 36: | Virtual [%] |
| | | Virtual | | | Virtual | |
| Written consent ^{&} | Х | | | | | |
| Verify eligibility | Х | | | | | |
| Teaching and First dose | Х | | | | | |
| administration and observation | | | | | | |
| Medical history, relapse | Х | Х | Х | Х | Х | Х |
| assessment | | | | | | |

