Safety Since this medication was extremely well-tolerated in several published studies,³⁴⁻⁵⁰ we anticipate the same will be true for people with MS. In prior studies, there was no effect of intranasal insulin on serum glucose levels. However, we will monitor the first 15 participants for a period of 90 minutes after their first dose of the medication to evaluate serial finger stick blood glucose levels. If there is a clinically significant reduction in these levels, we will convene a Data Safety Monitoring Board (DSMB) meeting to adjust the protocol. We will also record and, when appropriate, report all patient-reported adverse events, as described below. Subjects and their caregivers will be required to keep an electronic diary of adverse events, which will be reviewed at each study visit. As mandated by the FDA, the Columbia Suicide Severity Rating Scale will be administered at each study visit.

Cognitive Assessments The MACFIMS battery includes the following: The Symbol Digit Modalities Test (SDMT) is commonly used in MS to assess processing speed.^{1, 52-54} The oral version of the test is recommended for MS since the written version may be confounded by upper extremity weakness.^{53, 55, 56} There are three alternate versions of this test with strong psychometric properties.³⁷ A 3.5-4 point raw score difference on the SDMT has been identified as clinically meaningful.^{6, 57} The Controlled Oral Word Association Test (COWAT) measures phonemic fluency.⁵⁸ The California Verbal Learning Test, Second Edition (CVLT-II) is a verbal learning and memory test.^{55, 59} The Brief Visuospatial Memory Test – Revised (BVMT-R) is a visual, nonverbal test of learning and memory.⁶⁰ The Rao-version of the Paced Auditory Serial Addition Test (PASAT) evaluates processing speed, working memory, and basic addition skills.⁵⁸ Visual-spatial abilities are assessed with the Judgement of Line Orientation Test (JLO).^{58, 61} The Delis-Kaplan Executive Function System (DKEFS) tests executive functioning, concept formation, and cognitive flexibility.

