Safety/Adverse Event Monitoring An adverse event (AE) is any occurrence or worsening of an undesirable or unintended sign, symptom (or abnormal laboratory test), or disease temporally associated with the use of a medicinal product or intervention, whether or not it is considered related to the product/intervention. We will use the National Cancer Institute's Common Terminology Criteria for Adverse Events version 4.0 to report and grade all adverse events, whether or not they are related to disease progression or treatment. The relationship between an AE and the intervention will be determined by the blinded study physician and recorded on the appropriate form. The investigator will record all study adverse events in the chart and will treat participants with AEs appropriately, observing them until they resolve or stabilize. AEs will be collected from the start of the study until a participant terminates from the study; those that are unresolved at the time of termination will be followed until they resolve or up to 30 days. An adverse event is considered unexpected when its nature or severity is not consistent with the product information (e.g. protocol or the informed consent form). Serious AEs will be collected from informed consent signing until 30 days after study completion or until 30 days after a participant withdraws from the study. The following process for reporting a serious AE will ensure compliance with the International Conference on Harmonisation guidelines: the Institutional Review Board (IRB) and DSMB will be notified in two business days of a serious AE that is medication-related and unexpected, and standard reporting (15 calendar days) will occur if the event is serious, expected and medication-related, serious, expected and not medication-related, or serious, unexpected and not medicationrelated. Life-threatening events will be reported within 7 calendar days. Any pregnancy will be reported to the IRB and DSMB, and pregnancies will be followed to their conclusion. Female participants who become pregnant will stop the study intervention. The investigator will report pregnancies to the IRB within two business days. The study medication will be discontinued if an AE grade 3 or higher occurs and is at least possibly related to the medication or if the subject cannot tolerate the medication/ wants to discontinue it. Any death that is at least possibly related to the study will put the study on hold until the DSMB evaluates it.

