DSMB: The DSMB consists of an independent neurologist, an endocrinologist, and a statistician. It will convene any time an adverse event \geq grade 3 occurs and routinely at 25%, 50%, 75%, and 100% enrollment. All serious adverse events will be promptly and simultaneously reported to the IRB, the DSMB and the Independent Research Monitor. Only serious adverse events (SAEs) that would also meet the definition of an Unanticipated Problem Involving Risks to Subjects or Others (UPIRTSOs) that are related to the protocol will be promptly reported to the United States Army Medical Research and Materiel Command Office of Research Protections Human Research Protection Office HRPO (USAMRC ORP HRPO).

Independent Research Monitor: The PI, [name], has appointed [name], a trained neurologist, as the Independent Research Monitor. [name] will provide independent safety review and will have the

authority to stop the research study; remove an individual subject from the research study; and will take any steps to protect the safety and well-being of the subjects until the IRB can assess the problem or event. The independent research monitor must review all unanticipated problems involving risks to subjects or others (UPIRTSO), but not all SAEs. The monitor will review the SAEs if they also meet the definition of a UPIRTSO and will provide an unbiased written report of the event. The Research Monitor will comment on the outcomes of the event or problem and the relationship to participation in the study. Additionally, the research monitor will indicate whether she concurs with the details of the report provided by the principal investigator.

Analytic Plan

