Aim 1. Safety data will be analyzed as they are captured in real time. Assessments will focus on AEs (including study treatment tolerability assessments, laboratory evaluations, vital signs, and physical examination). The incidence rate of AEs will be recorded by system organ class, severity, and by relationship to the study treatment. Tolerability analysis will be based on the number (%) of subjects who failed to complete the study due to adverse events. Lab values for each parameter will be summarized by shift tables. For quantitative parameters, summary statistics for actual values and change from baseline will be presented. Changes in the first 24 weeks will be compared between groups using mixed effects regression analyses to account for the longitudinal nature of the data using random subject-specific intercepts and slopes.

Aim 2. Summary statistics (mean ± standard deviation, median and interquartile range, or number and percentages) will be used to characterize the outcomes. For each cognitive outcome, to evaluate variability in the estimated means across groups, assuming that the within-group means are normally distributed, a one-way ANOVA will be conducted at the follow-up visits during the first 24 weeks. If the within-group data are strongly non-Gaussian, a Kruskal-Wallis test will be used. A mixed effects longitudinal model will also be used to test whether any differences across groups exist at the follow-up visits within the first 24 weeks. Further, models accounting for covariates of interest, including the HOMA-IR, body composition, body mass index, age, sex and depression, will be used. For within-person changes in measures at follow-up compared to baseline, paired t-tests will be used. We will also evaluate the SDMT at each study visit and other MACFIMS outcomes at week48 to establish the longevity of any therapeutic response to insulin.

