#### III. Intervention

- a. Low dose Intranasal insulin 10 international units BID (LDINI)
- b. High dose Intranasal insulin 20 international units BID (HDINI)
- c. Placebo (PLAC)
- IV. Outcomes:
  - a. Primary outcome
    - i. Change from baseline in cognitive function as assessed by the Symbol Digit Modalities Test (SDMT) using raw scores
  - b. Secondary outcomes
    - i. Adverse events
      - Adverse events are defined as occurrence or worsening of an undesirable or unintended sign, symptom, or abnormal laboratory test potentially associated with INI. Adverse events for this study will consider: outcomes for which ≥5% experienced. Adverse events will be characterized overall and stratified by treatment arm).
      - 2. Evaluation of glucose levels (from finger-stick) for first 15 participants following first dose of medication.
      - 3. Number of adverse events comparing any INI versus placebo or HDINI versus LDINI versus placebo (e.g., two level any exposure to INI versus three level incorporating dosages).
    - ii. Change from baseline cognitive function in the tests listed below. Cognitive outcomes will be assessed as raw scores
      - 1. Change from baseline cognitive function in Controlled Oral Word Association Test (COWAT) assessing fluency (adjusted for form type)
        - a. Number of words produced in one minute for each of the three letters (raw score)
        - b. Number of words produced in one minute for each of the three letters (adjusted score)
      - 2. Change from baseline using Benton Judgement of Line Orientation (JLO) test assessing participant ability to match the angle and orientation in space
        - a. Total correct
      - 3. Change from baseline using PASAT-3 test assessing processing speed
        - a. Total correct
      - 4. Change from baseline using Brief Visuospatial Memory Test Revised (BVLT-R) assessing learning and memory. The following aspects from the BVLT-R will be considered.
        - a. Total recall
        - b. Delayed recall
      - 5. Change from baseline using Delis-Kaplan Executive Function System sorting (DKEFS) test for executive functioning. The following aspects from the DKEFS will be considered:
        - a. Total description score
        - b. Number of correct sorts
      - 6. Change from baseline using California Verbal Learning Test (CVLT) for learning and memory. The following aspects from the CVLT will be considered and combined into a composite outcome for CVLT using Z scores.

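### The Columbia suicide scale is given at all six visits, but no visible text plans a by-arm summary of it, and the SAP's 5% adverse-event rule makes no exception for suicidality

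*Protocol*

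**What the plan says.** **Collection.** The Safety paragraph under Outcomes in the protocol states: "As mandated by the FDA, the Columbia Suicide Severity Rating Scale will be administered at each study visit". The standard and the COVID-19 schedules both carry a row headed "Suicidality evaluation", marked at weeks 0, 6, 12, 24, 36 and 48. The virtual visits are included.

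**Protocol analysis.** Safety and tolerability are the primary objective. Aim 1 of the Analytic Plan opens with "Safety data will be analyzed as they are captured in real time". On adverse events it says: "The incidence rate of AEs will be recorded by system organ class, severity, and by relationship to the study treatment". That sentence sets no frequency cut and does not mention treatment arm. For laboratory data it says "Lab values for each parameter will be summarized by shift tables". It then promises summaries of quantitative parameters and a mixed-model comparison between groups of changes over the first 24 weeks. The Columbia scale is not named.

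**Monitoring.** The Safety/Adverse Event Monitoring section commits to grading and reporting all adverse events under CTCAE version 4.0. The DSMB section adds: "All serious adverse events will be promptly and simultaneously reported to the IRB, the DSMB and the Independent Research Monitor".

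**SAP.** Item IV.b.i.1 says: "Adverse events for this study will consider: outcomes for which ≥5% experienced". It then asks for adverse events overall and by treatment arm. Item IV.b.i.3 compares the number of adverse events between arms. Section VIII.h.i lists adverse events with no method beneath. Depression, sleep and quality of life each have an outcome in IV and a model in VIII. Suicidality has neither in the visible text. One part of the SAP, before section III, was not available for this review.

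**The concern.** A safety instrument completed up to six times per participant ought to yield a count by arm, even if that count is zero. As written, suicidality reaches the results only if it is recorded as an adverse event, and no visible text says that a positive response on the scale must be recorded as one. If it is recorded, the one visible output that shows event types by arm applies a 5% filter. Suicidal ideation or behaviour is the kind of event that can be uncommon and still matter, so a frequency filter suits it poorly. The analysis of the Beck Depression Inventory-II total score does not fill the gap, because a mean change in that score does not count participants with new ideation or behaviour.

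At stake is whether a reader of the results can see how many participants in each arm had new or worse suicidality. The protocol notes that intranasal insulin has not been studied in people with MS before, so this is information that the trial is meant to supply.

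**Working it through.** The documents give no figure for suicidality, so there is none to reproduce. The check is what the 5% rule does at the planned sizes.

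**Inputs.** 105 participants (Study Design), 35 per group (Sample Size and Power), 1:1:1 allocation (Study Treatment), hence 70 on insulin. The threshold is 5% (SAP IV.b.i.1). The SAP defines neither the denominator nor what counts as one outcome, so three denominators are tried, each with the rule applied per event term.

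**Cut-offs.** The smallest whole number at or above 0.05 × N:

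| Denominator | 0.05 × N | Needed to be shown | Most that can be left out |
|---|---|---|---|
| All participants, 105 | 5.25 | 6 | 5 (5/105 = 4.8%) |
| Pooled insulin, 70 | 3.5 | 4 | 3 (3/70 = 4.3%) |
| Within an arm, 35 | 1.75 | 2 | 1 per arm (1/35 = 2.9%) |

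**A lopsided example.** Five cases on insulin and none on placebo is 5/70 = 7.1% versus 0/35. With all 105 as denominator this is 4.8% and is dropped. With pooled insulin, 5 exceeds the cut-off of 4 and it is shown. Per arm, five cases across two arms put at least 3 in one of them (3/35 = 8.6%), and it is shown. So the example is hidden under one of the three readings only.

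**Illustration with assumed risks.** The documents give no risk, so 1%, 3% and 5% per participant are assumed, with full retention. The figure is the chance that at least one case occurs and the rule leaves it out.

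- All 105, same risk in every arm, P(1 ≤ X ≤ 5) with X ~ Bin(105, p): 65%, 86%, 57%.
- Pooled insulin, cases on insulin only, P(1 ≤ X ≤ 3) with X ~ Bin(70, p): 50%, 72%, 51%.
- Per arm, same risk in every arm, P(every arm ≤ 1) − P(no case) = [P(Bin(35, p) ≤ 1)]³ − (1 − p)^105: 52%, 33%, 10%.

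These show how far the answer depends on the denominator and the assumed risk. They are not forecasts. If the rule works per organ class, suicidality may pass the filter inside a larger class, but still without a line of its own.

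**The case against.** The strongest reply is that the protocol already covers this. The scale sits under Safety, and Aim 1 promises to analyse safety data. All adverse events are to be graded and reported with no frequency cut. Aim 1 closes with a between-group comparison of changes, and SAP IV.b.i.3 compares adverse-event counts by arm with no threshold of its own. The SAP is also silent on vital signs and laboratory shift tables, which the protocol plans, so its silence on one scale is weak evidence.

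Much of this stands. A reader might infer that suicidality would go undetected or unreported altogether; the documents do not support that, given the all-event grading and the reporting of serious events to the IRB, DSMB and Research Monitor. A reader might also infer that an excess such as 5/70 versus 0/35 would be hidden; that holds only if the denominator is all 105. The assumed risks have no anchor in the documents, and eligibility excludes current, active major depression, which may lower them.

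What does not stand is the step from these provisions to a by-arm count. The incidence sentence in Aim 1 does not say by arm. The between-group sentence most naturally concerns the quantitative parameters just before it, and a comparison of mean changes would not give a number of participants. SAP IV.b.i.3 is a total across event types. The objection that the 5% rule is a wider problem than suicidality is fair, but this is the event for which the trial gives a dedicated instrument at every visit.

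**Conclusion.** The point holds as a minor reporting gap on the protocol's primary objective. No visible text plans a by-arm summary of the Columbia scale, and the only visible by-event, by-arm adverse-event output can leave out up to 5 participants overall, 3 on insulin or 1 per arm, depending on a denominator that the SAP does not state. These counts assume the planned 35 per arm and the rule applied per event term. The probabilities are illustration only. The claim of absence is limited to the visible text, since part of the SAP could not be seen. No estimate, test, sample size or participant protection is affected.

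**What to change.** In SAP IV.b.i, and in a matching sentence under Aim 1, add a descriptive table by arm giving the number (%) of participants with suicidal ideation or behaviour on the Columbia scale that is new or worse than at week 0. Show weeks 0-24 (visits at weeks 6, 12 and 24) and weeks 24-48 (visits at weeks 36 and 48) separately, with a listing of each event. State that this table is exempt from the 5% rule and that no test will be done.

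The cost is one small table and a listing from data already collected. Estimates will be imprecise: 2/70 has an exact (Clopper-Pearson) 95% interval of 0.3% to 9.9%, and 0/35 has an upper limit of 1 − 0.025^(1/35) = 10.0%. That is a reason to keep the table descriptive, and no reason to leave it out.

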All study visits will be scheduled for the morning to reduce variability in cognitive function related to the time of day. At baseline, fasting laboratory testing will be performed, including a hemoglobin A1c test and insulin level. All subjects will then be given breakfast prior to completing cognitive testing. For follow-up visits, all subjects will complete the MACFIMS battery after eating a usual meal (if the participant came without having eaten, breakfast will be provided to them) and prior to taking the morning dose of study treatment. Unscheduled visits will occur if any safety issue arises.

In order to ensure subjects (or their responsible caregivers) are able to use the medication as instructed, all subjects and caregivers (when relevant) will be instructed on the use of the inhaler and will be observed by a health care provider when performing their first dose administration at the time of the first visit.

Risks

Intranasal insulin

Intranasal insulin has been shown to be safe and tolerable in other populations and patient groups, but it has never been studied in people with MS. The most common side effects related to irritation of the nasal passages. Giving insulin through the nose did not result in lower circulating glucose levels in other studies, but the first 15

people in this study will be monitored for this potential risk by testing a fingerstick blood glucose level periodically for 90 minutes after the first dose of intranasal insulin (see Safety section under **Outcomes** on page 10).

Insulin, given by the more traditional subcutaneous route, has the following potential risks:

Hypoglycemia: Common symptoms of hypoglycemia include sweating, dizziness or lightheadedness, shakiness, hunger, a fast heartbeat, tingling of the hands, feet, lips or tongue, trouble concentrating, confusion, blurry vision, slurred speech, anxiety, irritability, or mood changes, or headache. Very low blood sugar can cause loss of consciousness, seizures, or temporary or permanent brain problems or death. Mild hypoglycemia can be treated by drinking or eating something sugary right away (fruit juice, sugar candies, or glucose tablets).

Hypokalemia: Hypokalemia can lead to breathing problems, low heartbeat, or death.

Allergic reaction: Common symptoms of an allergic reaction include a rash all over the body, trouble breathing, a fast heartbeat, sweating, and feeling faint.

Weight gain or swelling of the arms and legs.

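### No planned safety analysis counts participants with hypoglycaemia symptoms, so a lower-grade insulin excess could be split across terms, dropped by the 5% rule or lost in the total

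*Protocol*

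**What the plan says.** **Objective.** The protocol (Objectives/Aims) makes safety and tolerability primary. The SAP (IV.b.i) lists adverse events among the secondary outcomes.

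**Risk.** Under Risks, the protocol describes nasal irritation as the most common effect of intranasal insulin and says other studies saw no fall in circulating glucose. It then lists risks of insulin by the subcutaneous route, with hypoglycaemia first: "Common symptoms of hypoglycemia include sweating, dizziness or lightheadedness, shakiness, hunger, a fast heartbeat, tingling of the hands, feet, lips or tongue", followed by further symptoms such as confusion, blurred vision, anxiety and headache.

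**Glucose.** In Outcomes, Safety: "we will monitor the first 15 participants for a period of 90 minutes after their first dose of the medication". The SAP (IV.b.i.2) repeats this: "Evaluation of glucose levels (from finger-stick) for first 15 participants following first dose of medication". Other glucose-related testing is at baseline: "At baseline, fasting laboratory testing will be performed, including a hemoglobin A1c test and insulin level". Neither visit schedule (standard or COVID-19) has a later glucose or safety-laboratory row.

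**Capture of later events.** "Subjects and their caregivers will be required to keep an electronic diary of adverse events, which will be reviewed at each study visit". Adverse events are also assessed at weeks 6 to 48, and unscheduled visits are allowed for safety issues.

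**Analysis.** Protocol, Analytic Plan, Aim 1: "The incidence rate of AEs will be recorded by system organ class, severity, and by relationship to the study treatment". The same paragraph promises laboratory shift tables and counts participants who leave because of adverse events. SAP IV.b.i.1: "Adverse events for this study will consider: outcomes for which ≥5% experienced". SAP IV.b.i.3 compares the number of adverse events by arm. SAP VIII.h.i names adverse events but gives no method.

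**The concern.** Hypoglycaemia is a syndrome. The protocol's list runs to about 13 symptoms across several body systems. Without a glucose value, a mild episode at home may be recorded as sweating in one participant, shakiness in another and hunger in a third. A table by organ class then shows several small rows. A 5% rule applied to each outcome may remove them, and a total of all events dilutes them. No planned table answers the plain question of how many participants in each arm had symptoms of hypoglycaemia.

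The primary objective is at stake. A statement that intranasal insulin is safe and tolerable in MS could be made without that number having been looked at.

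**Working it through.** **The plan's own figures.** The plan states no adverse-event rate and no safety power. Its nearby power figure (80% for a 6-point SDMT difference, SD 9, 35 per arm, two-sided 0.05) rebuilds to 79.6%. That confirms the arm size but has no bearing on safety.

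**Inputs from the documents.** 35 per arm, 1:1:1, so 70 insulin and 35 placebo. Twice-daily dosing for 24 weeks: 24 × 7 × 2 = 336 doses each.

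**Step 1: what the first-dose check can exclude.** Under 1:1:1 allocation about 10 of the first 15 receive insulin. With 0 events in 10, the one-sided 95% upper limit is 1 − 0.05^(1/10) = 25.9%. Even if all 15 received insulin it would be 1 − 0.05^(1/15) = 18.1%. The check covers 1 of 336 doses per monitored participant.

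**Step 2: what the 5% rule means.** The denominator is not stated.
- Overall: 0.05 × 105 = 5.25, so 6 participants.
- Insulin arms together: 0.05 × 70 = 3.5, so 4.
- One arm: 0.05 × 35 = 1.75, so 2.

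**Step 3: illustration.** Assumed, because the documents give no rates: 15% of insulin and 2% of placebo participants have symptomatic episodes. Each affected person reports 1 or 2 of k equally likely terms. Every participant also has an unrelated background probability b for each term.

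- Chance of any background symptom: B = 1 − (1 − b)^k.
- Grouped risk: B + (1 − B) × 0.15 on insulin, B + (1 − B) × 0.02 on placebo.
- Grouped power: exact binomial probability that a two-sided Fisher test of 70 vs 35 gives p < 0.05.
- Chance that no term reaches 6 of 105: simulation (4,000 to 40,000 trials per cell).

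| b | k | Grouped risk, insulin / placebo | Grouped power | No term reaches 6 of 105 (2 to 1 symptoms each) |
|---|---|---|---|---|
| 0 | 8 | 15.0% / 2.0% | 51% | 65% to 98% |
| 0 | 12 | 15.0% / 2.0% | 51% | 88% to 99.6% |
| 2% | 8 | 27.7% / 16.6% | 19% | 5% to 31% |
| 2% | 12 | 33.3% / 23.1% | 16% | 9% to 35% |
| 2% | 5 (narrow) | 23.2% / 11.4% | 26% | 2% to 22% |
| 5% | 8 | 43.6% / 35.0% | 12% | about 0% |
| 5% | 12 | 54.1% / 47.0% | 8% | about 0% |
| 5% | 5 (narrow) | 34.2% / 24.2% | 15% | about 0% |

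Hand check of one cell (b = 2%, k = 12, one symptom). The term rate is 0.02 + 0.98 × 0.15/12 = 0.0323 on insulin and 0.02 + 0.98 × 0.02/12 = 0.0216 on placebo. The expected count is 70 × 0.0323 + 35 × 0.0216, about 3.0. The chance of 6 or more is 0.082, and treating terms as independent, (1 − 0.082)^12 = 0.36. The simulation gives 0.35.

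**Step 4: other denominators.** With no background and 8 to 12 terms, no term is listed in about 15-87% of trials if 5% is counted in the 70 insulin participants, and in about 1-16% if any single arm suffices.

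**Step 5: grouped against single term.** Average power for a single term is at most about 7% in these settings and is below the grouped power in every row. Testing every term and taking the smallest p-value would find something more often, but that is unadjusted multiple testing and the plan does not propose it.

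**The case against.** The strongest case against is that the gap is narrower than it looks, and much of this stands.

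- **Capture is not limited to the diary.** A reader might infer that hypoglycaemia can appear only as diary symptoms. Visit assessments and unscheduled visits also capture events, and the adverse-event definition includes abnormal laboratory tests. These routes do not, however, schedule a glucose value.
- **Splitting is not inevitable.** The investigator records events, and may enter one hypoglycaemia event for a cluster of symptoms. Nothing requires this.
- **Serious events are protected.** A reader might infer that dangerous hypoglycaemia could go unreported. Serious events are reported individually, and any event of grade 3 or higher convenes a DSMB that includes an endocrinologist.
- **An unsplit comparison exists.** SAP IV.b.i.3 compares total events by arm. It pools every kind of event and has no stated method.
- **Background symptoms weaken the contrast.** Dizziness, tingling, confusion and blurred vision also occur in MS. Once background is allowed for, some term is usually listed, and grouped power drops sharply. The no-background figures alone would overstate both the problem and the remedy.
- **The listed risk belongs to another route.** The protocol attaches hypoglycaemia to subcutaneous insulin and expects little of it here. It still chose to check glucose in the first 15 participants, so it did not treat the question as closed.

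**Conclusion.** The point holds for lower-grade, non-serious episodes. After the first-dose window no glucose measurement is scheduled, and no stated analysis counts participants with hypoglycaemia symptoms. Unless the investigator records a single hypoglycaemia event, an excess can be split across terms, filtered by the 5% rule or diluted in the total.

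The size depends on assumed rates and on an unstated denominator. With an overall 5% and no background, non-listing is the likely outcome (about 65% to over 99%). With a 2% background per term it is about 5-35%. With 5% background some term is always listed, and the problem becomes low power per row. The grouped count does better than the average single term throughout, but at 8-26% power once background is present it supports estimation rather than a test.

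A reader might go further and conclude that safety would rest on 15 monitored first doses. The documents do not support that: event tables, the total count, withdrawals due to adverse events and DSMB review all contribute.

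**What to change.** In SAP IV.b.i and VIII.h.i, pre-specify one grouped outcome from the adverse-event and diary records already collected:

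- **Narrow definition (main):** an event recorded as hypoglycaemia or low glucose, or new or worsened sweating, shakiness, hunger or fast heartbeat.
- **Broad definition (sensitivity):** any symptom in the protocol's hypoglycaemia list.
- **Counting:** each participant once, weeks 0 to 24, exempt from the 5% rule.
- **Reporting:** n (%) by arm, and the risk difference with exact 95% confidence interval for any INI vs PLAC and for each dose vs PLAC.
- **Timing:** fix both term lists before unblinding.

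Also state the denominator of the 5% rule, give SAP VIII.h.i a method, and reconcile the laboratory shift tables promised in Aim 1 with the visit schedules, which contain no follow-up safety-laboratory row. A similar group for nasal events is optional, since no defect in their handling is shown.

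The cost is SAP wording and one table, with no new data. Some background MS symptoms will be counted, the narrow group will miss episodes felt only as, say, dizziness or confusion, and power stays limited, so the result should be read as an estimate. No change to monitoring, dosing or stopping is proposed.
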